16 MEASUREMENT OF EFFECT

Nicotine boost will be measured as the post-bout saliva nicotine concentration minus the pre-bout saliva nicotine concentration.

Subjective questionnaires are scored on a 0-100 visual analog scale (some exceptions, such as -100 to 100) or a Likert scale (varying amount of points). Subjective responses will be evaluated based on their change from pre- to post-bout and for differences between products.

17 SAFETY EVALUATION

17.1 Safety Monitoring

Subjects will be monitored for safety during product use sessions by trained laboratory staff. Participants are able to use the study products ad lib and can stop product use at any time without being withdrawn from the study completely. Subjects will be given phone numbers for research associates and supervising physicians to call if there are adverse effects or other study-related problems. Subjects will be advised that if they have any adverse effects and/ or wish to stop participating in the study for any reason, they are free to do so.

The data collected from this study will be organized by a unique identification number assigned to the participant so that their identity will be available only to project staff and will remain completely confidential. The clinical study coordinator and staff and PI of the study will have access to the data records. All study records will be kept electronically in Roswell Park Comprehensive Cancer Center maintained and secured equipment. Any data, specimens, forms, reports, and other records that leave the site will be identified only by a participant identification number (Participant ID, PID) to maintain confidentiality. All records will be kept in a limited access environment. All computer entry and networking programs will be done using PIDs only. Information will not be released without written authorization of the participant.

17.2 Unanticipated problems

An Unanticipated Problem (UP) is any incident, experience, or outcome that meets all of the following criteria:

- Unexpected (in terms of nature, severity, or frequency) given:
 - The research procedures that are described in the study-related documents, including study deviations, as well as issues related to compromise of participant privacy or confidentiality of data.
 - The characteristics of the participant population being studied.
- Related or possibly related to participation in the research (possibly related means there is a reasonable possibility that the incident, experience, or outcome may have been caused by the procedures involved in the research).
- Suggests that the research places participants or others at a greater risk of harm (including physical, psychological, economic, or social harm) than was previously known or recognized or if in relation to an AE is deemed Serious.

17.3 Reporting Unanticipated Problems

The Reportable New Information (RNI) Form will be submitted to the CRS Quality Assurance (QA) Office within 1 business day of becoming aware of the Unanticipated Problem. After review, CRS QA Office will submit the RNI to the IRB.

When becoming aware of new information about an Unanticipated Problem, submit the updated information to CRS QA Office with an updated Reportable New Information Form. The site Investigator or designated research personnel will report all unanticipated problems to the IRB in accordance with their local institutional guidelines.

Roswell Park Protocol No.: I-3234822

18 DATA MANAGEMENT AND CONFIDENTIALITY

To ensure data security and confidentiality, all assessments will be administered by trained research study staff. Data management activities will be performed using REDCap (Research Electronic Data Capture). REDCap is a secure web-based application that supports data capture and management for research studies. In the event of REDCap being inaccessible for a study visit, paper copies of the questionnaires will be administered to the participant at that point in time and data entry will be performed by the assigned Senior Research Associate after the study session is completed. Data can be entered and changed only by those with the rights to do so. All participant records and data will be held in the Health Behavior Department at Roswell Park Comprehensive Cancer Center. All personnel involved in the conduct of this study are Roswell Park staff.

- Access to the data by all necessary research personnel will be through a password protected network computer. At no time will data be downloaded on a thumb drive or other portable media or laptop.
- Participant identity will not be disclosed in the event of publication or sharing of data.
- Any paper files containing identifiers (if applicable to the research) will not be taken off Roswell Park premises; they will be kept in a locked filing cabinet in a secure building on the Roswell Park campus.
- PHI will not be re-used or disclosed for purposes other than research use.
- PHI (limited data set) may be shared with the partner site (URMC) to facilitate study recruitment and data analysis.
- Essential documents will be retained per Roswell Park's policy for 6 years from the study termination date. These documents could be retained for a longer period, however, if required by the applicable local regulatory requirements or by an agreement with Roswell Park.

18.1 Data Collection

Data management activities are performed using REDCap.

18.2 Maintenance of Study Documents

Essential documents will be retained per Roswell Park's policy for 6 years from the study termination date. These documents could be retained for a longer period, however, if required by the applicable local regulatory requirements or by an agreement with Roswell Park.

18.3 Revisions to the Protocol

Roswell Park may make such changes to the protocol as it deems necessary for safety reasons or as may be required by the U.S. FDA or other regulatory agencies. Revisions will be submitted to the IRB/ERC for written approval before implementation.

18.4 Termination of the Study

It is agreed that, for reasonable cause, either the Roswell Park Investigators or the Sponsor, may terminate this study, provided a written notice is submitted within the time period provided for in the Clinical Trial Agreement. In addition, Roswell Park may terminate the study at any time upon

Roswell Park Protocol No.: I-3234822

immediate notice if it believes termination is necessary for the safety of participants enrolled in the study.

19 STATISTICAL PLAN

This is an open-label, factorial-design, multi-center study of e-liquid composition and effects on vaping topography.

19.1 Sample Size Determination

The planned sample size is n=72 evaluable patient, who are expected to complete 7 potential sessions, for a total of 504 observations.

However, we anticipate an attrition rate of 5-10% per session and the table below provides expected sample sizes under differing rates of attrition:

Session		1	2	3	4	5	6	7
Subjects Completed	5% Attrition	72	68	65	62	59	56	53
	10% Attrition	72	65	58	52	47	43	38
	5% 1-3 and 10% in 4-7	72	68	65	58	53	47	43

A conservative sample size calculation is based on comparing any two flavors or nicotine formulations using a two-sided paired t-test. The minimum expected sample size per combination is expected to be between 38 and 53; which provides 80% power (at $\alpha=0.05$) to detect a difference of at least 0.47 and 0.39 standard deviations. Since the actual models used in the analysis will account for additional sources of variability and will borrow information across sessions, the actual detectable effect sizes may be larger.

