8 STUDY ENDPOINTS

8.1 Primary Endpoints

The primary endpoints are measures of vaping topography [(per-puff volume, inter-puff interval, peak flow rate, puff count, total volume (sum of volumes across all puffs)], which are treated as quantitative outcomes and will be summarized by:

- Condition (flavor or nicotine composition) and,
- Bout (directed or ad-lib) using the appropriate descriptive statistics.

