10 STUDY INTERVENTION

Participants will vape twice per session – once directed and once ad lib. In the directed bout, participants are instructed to take a 4 second puff on the device every 60 seconds until a total of 8 puffs are completed. In the ad lib bout, participants are free to puff as they like for a defined 15 minute period.

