Vape assembly and puffing regimen will also be directed by the experimenter. The device used will be a SmokTech® NORD2 or equivalent device. These sessions will be approximately 90 minutes long.

Sessions 6-7: Relationship of nicotine formulation to vaping topography and sensory evaluation.

In this condition, we will use a 2 (nicotine form) x 2 (ad lib vs directed) within-subjects design. All liquids will have a 60/40 carrier concentration and 5% nicotine. The primary comparison is between 5% synthetic nicotine and 5% tobacco-derived nicotine.

Over 2 laboratory sessions (sequence determined by A/B design), participants will complete ad lib and directed bouts (sequence determined by A/B design) using each liquid form. After each vape, participants will complete a battery of sensory outcome measures. All questionnaires will be administered by the experimenter.

Vape assembly and puffing regimen will also be directed by the experimenter. The device used will be a SmokTech® NORD2 or equivalent device. These sessions will be approximately 90 minutes long.

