19.4 Primary Analysis

The primary objective is to evaluate the influence of:

Roswell Park Protocol No.: I-3234822

- a. tobacco flavoring composition on vaping topography
- b. synthetic vs. tobacco derived nicotine on vaping topography

The primary endpoints are measures of vaping topography, which are treated as quantitative outcomes and will be summarized by condition (flavor or nicotine composition) and bout (directed or ad-lib) using the appropriate descriptive statistics.

Using data from sessions 1-5, each endpoint will be modeled as a function of flavoring (own, none, and 3 commercial flavors), bout (directed or ad-lib), their two-way interaction, and random subject and site effects using a linear mixed model. Tests about the appropriate contrasts of model estimates will be used to compare:

- i) mean differences between flavors within a type of bout,
- ii) mean differences between bouts within a flavor,
- iii) effects of bout (ad lib – directed) between flavors,
- iv) effect of flavor between bouts.

Using data from sessions 6 & 7, each endpoint will be modeled as a function of nicotine composition (synthetic vs. tobacco derived), bout (directed or ad-lib), their two-way interaction, and random subject and site effects using a linear mixed model. Tests about the appropriate contrasts of model estimates will be used to compare:

- i) mean differences between composition within a type of bout,
- ii) mean differences between bouts within a composition,
- iii) effects of bout (ad lib – directed) between compositions,
- iv) effect of composition between bouts.

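### Section 19.1 powers one unadjusted paired comparison, but Section 19.4 tests several contrasts on five unranked primary endpoints with no deciding bout, testing order or multiplicity adjustment.

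*Combined protocol and SAP*

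**What the plan says.** - **Sample size (Section 19.1).** "A conservative sample size calculation is based on comparing any two flavors or nicotine formulations using a two-sided paired t-test". After attrition the plan counts on 38 to 53 pairs, and 80% power at alpha 0.05 is claimed for 0.47 and 0.39 SD. No endpoint or bout is attached. The section calls the calculation conservative, then closes by saying that under the actual models "the actual detectable effect sizes may be larger".
- **Endpoints (Section 8.1).** Five topography measures are all primary: "per-puff volume, inter-puff interval, peak flow rate, puff count, total volume". None is ranked above another.
- **Analysis (Section 19.4).** One mixed model covers sessions 1–5 and another covers sessions 6–7, each fitted to every endpoint. Under each model, "Tests about the appropriate contrasts of model estimates will be used to compare" introduces four contrast types: products within a bout, bouts within a product, bout effects between products, and product effects between bouts.
- **Partial guidance (Section 11.3).** For sessions 6–7, "The primary comparison is between 5% synthetic nicotine and 5% tobacco-derived nicotine". For sessions 2–5, three commercial tobacco variants are set against one unflavored liquid. Neither statement fixes an endpoint or a bout, and Section 19.4 carries neither forward as a priority.
- **The two bouts (Section 10).** In the directed bout participants "take a 4 second puff on the device every 60 seconds until a total of 8 puffs are completed". In the ad lib bout they puff freely for 15 minutes.

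**The concern.** The stated alpha and power describe one test, whereas a positive primary result could come from any of many. Two things are at stake. First, at 0.05 per test, the chance of at least one false primary finding is well above 5% for each objective. Second, a reader cannot tell which endpoint and bout were meant to decide either objective, so a choice made after seeing the data would still comply with the plan. The bout matters in substance: puff length, spacing and count are instructed in the directed bout, so puff count and inter-puff interval there largely reflect the instruction.

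**Working it through.** **1. Inputs.** 38 and 53 pairs (session 7 at 10% and 5% attrition), and 47 and 59 pairs (session 5, same rates), from the Section 19.1 table. Two-sided alpha 0.05 and 80% power, from Section 19.1. Five endpoints, from Section 8.1. Four randomised liquids and two nicotine forms, from Section 11.3. The correlation between endpoints is not in the documents; one common value of 0, 0.5 or 0.8 is assumed.

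**2. The plan's own figure.** Paired t-test, noncentral t with df = n − 1 and noncentrality d√n, where d is in SDs of the paired difference. At alpha 0.05 and 80% power, n = 38 gives d = 0.467 and n = 53 gives d = 0.392. Section 19.1 is arithmetically right.

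**3. How many tests.** If every pairwise contrast is meant, the third and fourth contrast types are the same interaction contrasts, so there are three distinct kinds. Per endpoint, the flavor model (five levels with own brand) has 20 + 5 + 10 = 35 distinct contrasts and the nicotine model 2 + 2 + 1 = 5. Over five endpoints that is 5 × 40 = 200. The error rates below use a much narrower set: product comparisons in one bout, without own brand.

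**4. Chance of at least one false finding, no liquid differing, 0.05 per test, one bout, five endpoints.** For nicotine with independent endpoints this is exact: 1 − 0.95⁵ = 0.226. The rest are simulated with paired t-tests (38 pairs for nicotine, 47 for flavor); repeated runs agree to about one percentage point.

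| Tests | Corr. 0 | Corr. 0.5 | Corr. 0.8 |
|---|---|---|---|
| Nicotine, 1 × 5 | 23% | 19% | 13% |
| Flavor versus unflavored, 3 × 5 | 48% | 42% | 30% |
| All flavor pairs, 6 × 5 | 68% | 58% | 44% |

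**5. With Holm across five endpoints** (one nicotine test each, or one 3-df flavor test each), the simulated chance is about 3–5% for each objective. Over both objectives the bound is 0.05 + 0.05 = 10% (1 − 0.95² = 9.75% if independent).

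**6. What that costs in power.** Holm's strictest step is 0.05/5 = 0.01.
- Nicotine: detectable 0.581 SD (n = 38) and 0.485 SD (n = 53). Power at the plan's 0.47 and 0.39 SD falls to 58% and 57%.
- 3-df flavor test: F with 3 and 3(n − 1) df, compound symmetry assumed. If one liquid differs from the other three by d, the noncentrality is 1.5nd², giving 0.478 SD (n = 47) and 0.425 SD (n = 59). If only two extremes differ, with the other two midway, it is nd², giving 0.585 and 0.520 SD.
- If the three flavor-versus-unflavored contrasts replace the 3-df test, the family is 3 × 5 = 15 tests and the strictest step is 0.05/15 = 0.0033. The formula in step 2 then gives 0.58 SD (n = 47) and 0.51 SD (n = 59).

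**The case against.** The best case for the plan is that this is a laboratory study whose objectives are to examine influences. It claims no familywise control and sets out to report every endpoint by condition and bout. It also gives more direction than Section 19.4 alone suggests, since Section 11.3 names the nicotine comparison as primary and gives flavor an unflavored reference. Two separate objectives can reasonably carry separate alphas.

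Much of this stands. Separate alpha per objective is defensible if stated, and the flavor reference lowers the relevant flavor error rate from 44–68% to 30–48%. It does not remove the gap: the objectives and endpoints are labelled primary, alpha and power are stated, and endpoint and bout stay open.

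Three stronger readings are tempting but unsupported.

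- **That a false positive is near certain because there are 200 tests.** The plan says only that appropriate contrasts will be tested, the tests are correlated, bout-within-product contrasts answer neither primary objective, and some directed-bout outcomes barely vary. The count is an upper listing and gives no error rate.
- **That the sample size calculation is wrong.** It reproduces; what is missing is its link to the analysis.
- **That the closing remark about larger detectable effects is an error, because borrowing information must help.** That needs equal, independent residuals in both bouts, which the documents do not support. With a residual pooled over bouts and ad lib variance k times directed variance, the model's standard error for a directed-bout comparison is about √((1 + k)/2) times the paired test's: about 1.2 for k = 2 and 1.6 for k = 4. Detectable effects could therefore be larger, as the plan says. What remains is a question of wording: how the calculation can be conservative if the real detectable effects may be larger.

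**Conclusion.** The concern holds in this form: Section 19.1's alpha and power belong to one unadjusted paired comparison, and the plan does not say which endpoint, bout or contrast that is. Followed as written at 0.05 per test, one bout alone carries a false-finding chance of about 13–23% for nicotine and, for flavor, 30–48% or 44–68% depending on whether the unflavored reference or all pairs are used. These rates assume that no liquid differs and that the endpoints share one common correlation between 0.8 and 0. The true correlations are unknown; total volume, being the sum of puff volumes, is certainly related to other endpoints. The 58% and 57% power figures apply only at Holm's strictest step; later steps are less strict. The design remains usable. This should be settled before analysis, but it does not invalidate the study.

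**What to change.** 1. **Section 19.4, deciding tests.** For each objective name one deciding bout. Ad lib is the natural choice because the directed bout instructs puffing, but the sponsor may prespecify otherwise. Name one condition test per endpoint: for nicotine, the comparison already given in Section 11.3; for flavor, a 3-df test among the four randomised liquids. Prespecified flavor-versus-unflavored contrasts are an alternative, provided all 15 enter the Holm family. Apply Holm across the tests within each objective, and state that alpha is controlled per objective, not study-wide (about 10% at most over both).
2. **Section 19.4, everything else.** Report all remaining contrasts, including those in the other bout, as supportive estimates without familywise control.
3. **Section 19.1.** State that 0.47 and 0.39 SD apply to one unadjusted comparison. Add the alpha 0.01 figures: nicotine 0.58 SD (n = 38) and 0.485 SD (n = 53); 3-df flavor test 0.48–0.59 SD (n = 47) and 0.43–0.52 SD (n = 59), compound symmetry assumed. Ask the sponsor to reconcile the description of the calculation as conservative with the closing remark that "the actual detectable effect sizes may be larger".

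**Cost.** Text changes in two sections, less favourable stated detectable effects and fewer confirmatory contrasts. No extra participants or visits.

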19.2 Randomization

Subjects will complete up to 7 sessions. At each session, subjects will complete directed and ad lib bouts of vaping. The order of directed and ad lib bouts will be randomized within participant using a permutation block design (block sizes of 2 and 4).

Session 1 will use their own-brand liquid. No randomization is required.

Sessions 2-5 will evaluate the relationship of tobacco flavor formulation (no flavor and 3 commercial flavor variants) on outcomes. The order of nicotine forms (i.e., what flavor is experienced at a given session) will be randomized using a permuted Latin Square design.

Sessions 6-7 will evaluate the relationship of nicotine formulation (2 forms) on outcomes. The order of nicotine forms will be randomized using a permuted Latin Square design.

19.3 Demographics and Baseline Characteristics

Descriptive statistics (as appropriate: n, percent, mean, median, min and max) will be used to summarize demographic and baseline characteristics.

19.4 Primary Analysis

The primary objective is to evaluate the influence of:

Roswell Park Protocol No.: I-3234822

- a. tobacco flavoring composition on vaping topography
- b. synthetic vs. tobacco derived nicotine on vaping topography

The primary endpoints are measures of vaping topography, which are treated as quantitative outcomes and will be summarized by condition (flavor or nicotine composition) and bout (directed or ad-lib) using the appropriate descriptive statistics.

Using data from sessions 1-5, each endpoint will be modeled as a function of flavoring (own, none, and 3 commercial flavors), bout (directed or ad-lib), their two-way interaction, and random subject and site effects using a linear mixed model. Tests about the appropriate contrasts of model estimates will be used to compare:

- i) mean differences between flavors within a type of bout,
- ii) mean differences between bouts within a flavor,
- iii) effects of bout (ad lib – directed) between flavors,
- iv) effect of flavor between bouts.

Using data from sessions 6 & 7, each endpoint will be modeled as a function of nicotine composition (synthetic vs. tobacco derived), bout (directed or ad-lib), their two-way interaction, and random subject and site effects using a linear mixed model. Tests about the appropriate contrasts of model estimates will be used to compare:

- i) mean differences between composition within a type of bout,
- ii) mean differences between bouts within a composition,
- iii) effects of bout (ad lib – directed) between compositions,
- iv) effect of composition between bouts.

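### Section 19.4 models positive topography endpoints additively, with no scale or bout-specific variance named, across two bouts that differ in level by design

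*Combined protocol and SAP*

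**What the plan says.** Section 8.1 lists five primary endpoints: "per-puff volume, inter-puff interval, peak flow rate, puff count, total volume (sum of volumes across all puffs"). Section 19.4 says that "The primary endpoints are measures of vaping topography, which are treated as quantitative outcomes". Each is modelled on liquid (flavor, or nicotine form), bout, "their two-way interaction, and random subject and site effects using a linear mixed model". The contrasts are additive: "mean differences between flavors within a type of bout" is the liquid contrast, and "effects of bout (ad lib – directed) between flavors" is a difference of differences. The nicotine model repeats the set, ending with "iv) effect of composition between bouts".

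The two bouts are set up differently in section 10. For the directed one, "participants are instructed to take a 4 second puff on the device every 60 seconds until a total of 8 puffs are completed". For the other, "In the ad lib bout, participants are free to puff as they like for a defined 15 minute period".

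No transformation, link function, count model, residual check or variance structure by bout appears anywhere. The plan does not use the words raw scale or common variance; they are the plain reading of an unqualified linear mixed model.

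**The concern.** All five endpoints are positive, and measures of this kind often vary more where their level is higher. The two bouts share one model, and the amount of puffing in one of them is fixed. If the standard deviation rises with the mean, a single residual variance is an average that fits neither bout. It is too small for ad lib, where liquid differences would be declared too readily, and too large for directed, where real differences would be missed. Both kinds of contrast are primary.

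The interaction contrasts (iii and iv) raise a second question. On an additive scale, a liquid that raises volume by the same percentage in both bouts has a non-zero interaction whenever the bout means differ. A reader could take that as a behavioural difference between bouts.

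**Working it through.** **The plan's own figure.** Section 19.1 gives 80% power for 0.47 and 0.39 SD at n = 38 and 53. Attrition: 72 × 0.90⁶ = 38.3 and 72 × 0.95⁶ = 52.9. The noncentral-t calculation for a two-sided paired t-test at 0.05 gives 0.467 and 0.392. The figures reproduce, but they are in SD units and do not say on which scale.

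**Inputs from the documents.** The Background gives 112.15 ± 18.9 mL and 37.94 ± 7.67 mL/s for experienced users, so the coefficients of variation are 18.9/112.15 = 0.17 and 7.67/37.94 = 0.20. These come from a literature summary and carry no skewness, median or range. No ad lib/directed ratio is given.

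**Assumptions.** Data are log-normal. Log-SDs for subject, session and residual are 0.2/0.1/0.15 (mild), 0.4/0.15/0.25 (moderate), 0.6/0.2/0.35 (strong) and 0.8/0.25/0.5 (very strong). The ad lib/directed mean ratio is m. Two liquids are compared; site and the own-brand session are omitted.

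**Step 1: error bars on the raw scale.** Put the directed mean at 1 and let V, τ² and ε² be the subject, session and residual variances at that level. The correct per-subject variance of a liquid difference is 2(τ² + ε²) in the directed bout and 2m²(τ² + ε²) ad lib. A model with a subject intercept and one residual variance uses 2s² for both, where

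s² = V(m − 1)²/3 + τ²[(1 + m²)/2 − m/3] + ε²(1 + m²)/2.

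- Moderate spread: V = 0.1735, τ² = 0.0267, ε² = 0.0774. At m = 2, s² = 0.0578 + 0.0490 + 0.1935 = 0.3003. The correct values are 0.1041 (directed) and 4 × 0.1041 = 0.4164 (ad lib).
- The ad lib standard error is √(0.3003/0.4164) = 0.85 of its proper size, so a nominal 5% test rejects when |Z| > 1.96 × 0.85 = 1.67, about 9.6%.
- The directed standard error is √(0.3003/0.1041) = 1.70 times its proper size.
- At m = 1, s² = 0.0952 against 0.1041, which gives about 6.1%. That remainder comes from the missing session term, not from the scale.
- Mild spread at m = 2: V = 0.0408, τ² = 0.0105, ε² = 0.0239, so s² = 0.0926 against 0.0344 and 0.1375. The ratios are 0.82 (ad lib) and 1.64 (directed), and ad lib type I error is about 10.8%.

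Simulation of the moderate case at n = 47 agrees: ad lib type I error near 9.5% raw against about 5.5% logged.

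**Step 2: power.** With effects set at 0.47 or 0.39 SD on the log scale, the paired ad lib contrast has 78–82% power logged. Raw, it has:

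| Spread | Raw-scale power |
|---|---|
| mild | 76–78% |
| moderate | 71–74% |
| strong | 61–67% |
| very strong | 51–57% |

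With one pooled variance (mild, strong and very strong spreads), the raw directed contrast falls from 53–82% at m = 1 to 13–34% at m = 2, against about 81–86% logged.

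**Step 3: total volume.** At n = 47, with moderate spread and a 15% per-puff effect, directed-bout power is under 1% raw and about 25% logged; the latter depends on the assumed spread of ad lib puff counts. Logging alone is not enough, because the ad lib bout carries count variation that the directed bout does not. With its own variance, the directed log contrast has standard error √(2 × 0.085/47) = 0.060, where 0.085 = 0.15² + 0.25². Then ln 1.15/0.060 = 0.140/0.060 = 2.32, and power is about Φ(2.32 − 1.96) = 64%.

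**Step 4: interaction.** With directed mean 100 and a common liquid ratio r, the additive interaction is 100(m − 1)(r − 1): 20 at m = 2 and r = 1.2, zero at m = 1. Simulated rejection with one pooled variance was 3–11% at the moderate-spread settings run. Over the other three spreads it was 7–18% at m = 2 and 13–32% at m = 3, against 2–4% logged.

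**The case against.** Four objections have force.

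- **Skew is not documented.** The only spreads given correspond to coefficients of variation near 0.2, and there the paired loss is 2 to 3 points. This stands for the part of the loss due to skew. It does not remove the variance problem: Step 1 shows that the mismatch follows from the bout ratio and persists at mild spread. In the pooled model at mild spread and m of 1.5 or more, raw ad lib power looks no worse (87–89% against 83–85% logged), but that comes with an inflated error rate.
- **The bout ratio is known to differ only for amount of puffing.** Nothing in the documents shows that per-puff volume or peak flow differs between bouts. This stands, and it is why total volume is the clearest case.
- **An additive interaction is a legitimate estimand.** The Background frames the regulatory question in mL and yields. The problem is also symmetric: with an equal absolute effect and m = 2, a log-scale interaction test rejected 17–27% of the time. This stands.
- **The equal-percentage argument cannot reach every endpoint.** The directed bout fixes puff count and spacing by instruction, so a liquid cannot change them proportionally in both bouts, and logging does not remove that interaction. This stands.

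A reader might infer that contrasts iii and iv will routinely report a spurious interaction on all five endpoints, or that the data are known to be right-skewed. The documents support neither.

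**Conclusion.** The plan leaves the scale and the variance structure of its primary models unstated. The default reading fits poorly if spread grows with level. Under that assumption and m = 2, ad lib type I error roughly doubles from nominal, to about 9.5–11%, and directed liquid contrasts lose most of their power. Total volume in the directed bout is the worst case. The loss due to skew alone runs from 2–3 points at mild spread to nearly 30 at very strong spread.

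The interaction point is secondary. It concerns per-puff volume, peak flow and total volume only, needs different bout means, is not frequent in the planned model at moderate spread, and turns on which estimand is wanted.

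All sizes rest on assumed log-normal spreads and bout ratios. This is a worthwhile low-cost improvement rather than an error that invalidates the analysis. Settling it beforehand also avoids choosing a scale for five primary endpoints after the data are seen.

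**What to change.** In section 19.4:

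- Pre-specify log-transformed per-puff volume, peak flow and total volume, with residual variance allowed to differ by bout, and report liquid effects as ratios.
- Analyse puff count (log-link negative binomial mixed model) and inter-puff interval (log) in the ad lib bout only, without contrasts iii and iv.
- State how a bout with no puffs enters the total-volume analysis. Section 17.1 lets participants stop product use at any time, and the log of zero is undefined.
- Keep the raw-scale model as a sensitivity analysis, so that absolute mL differences are still reported.

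The cost is SAP wording and a few lines of code. The downside is that primary effects become ratios rather than mL differences, which is less direct for the yield question in the Background; the sensitivity analysis covers that.
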